KZR-261 was not genotoxic when tested in the in vitro mutagenicity (Ames) test, in vitro chromosomal aberration assay, and in vivo micronucleus assay in rats.

To further understand the effect of KZR-261 on fasting glucose levels, non-GLP repeat-dose studies were conducted in monkeys in which the rate and schedule of administration was varied. Increased hyperglycemia did not appear to correlate with increased exposure but did correlate with decreased food-induced insulin secretion. Administration of KZR-261 as a 30-minute IV infusion rather than an IV bolus reduced elevations in glucose, triglycerides, lipase, pancreatic elastase 1, and amylase levels. Hyperglycemia observed with weekly dosing was also attenuated when the same dose was administered biweekly (Q2W). These findings suggest that pancreatic toxicity can potentially be attenuated by delivering KZR-261 via a 30-minute infusion, thus lowering the maximum plasma concentration (C_{max}), or by decreasing the frequency of the dose administration.

In summary, KZR-261 showed minimal off-target activity, no inhibition of hERG, and did not induce cardiovascular or respiratory toxicity in vivo. The starting dose for this Phase 1 human study is 1.8 mg/m² (1/10th of the STD₁₀ in rats, the most sensitive species) infused over 30 minutes.

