3.2.1.1. Dose Level Escalation for Each Cohort (X+1)

Increments in dose escalation or whether to de-escalate will be based on review of emerging safety data by a SRC composed of study Investigators and Sponsor representatives ([Section 3.5](#)). At a minimum, the SRC will convene upon completion of each successive cohort. The SRC will review safety and available PK data from subjects enrolled to the most recently completed dose cohort who have completed the DLT assessment period. Dose increments for the next cohort will be determined based on the following criteria:

Up to a 100% dose increment may occur if:

- no subject in the most recent cohort required dose reduction for purposes of managing AEs and/or laboratory abnormalities;
- no subject experienced AEs greater than Grade 2 in severity;
- no subject exhibited one or more treatment-emergent serum amylase or lipase $>1.5 \times$ the upper limit of normal (ULN) lasting longer than 72 hours after dosing;

- no subject exhibited fasting blood sugar (FBS) >200 mg/dL on 2 consecutive measures over a 72-hour period after dosing; or
- no subject exhibited FBS >160 mg/dL three or more times over a 72-hour period after dosing.

Up to a 50% dose increment may occur if:

- no subject in the most recent cohort required dose reduction for purposes of managing AEs and/or laboratory abnormalities;
- there is resolution of any \geq Grade 3 AE to Grade 1 or baseline in ≤ 10 days

Up to a 33% dose increment may occur if:

- no subject in the most recent cohort required dose reduction for purposes of managing AEs and/or laboratory abnormalities;
- there is no resolution of any \geq Grade 3 AE to Grade 1 or baseline within 10 days.

AEs for dose increment decisions must be treatment-emergent and considered at least possibly related to KZR-261.

Lower dose increases (ie, 25% increase or $1.25 \times$ *current dose*) may be considered based on the frequency and severity of AEs not described above that are at least possibly related to KZR-261.

If a DLT necessitates enrollment of additional subjects into a cohort, all safety data for that cohort will be reviewed after the additional subjects have completed the DLT assessment period. Based on evaluation of the data, the SRC and/or Sponsor may decide to enroll subjects at a KZR-261 dose level that is intermediate between the previous and the next higher planned dose.

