- Drug-induced liver injury (Hy's law), including all of the following: greater than $3 \times$ ULN elevation in aspartate aminotransferase (AST) and/or alanine aminotransferase (ALT), total bilirubin $>2 \times$ ULN in the absence of findings of cholestasis (ie, absence of alkaline phosphatase elevation to $>2 \times$ ULN) AND no other etiology to explain the combination of increased ALT/AST and total bilirubin.
- FBS >200 mg/dL on 2 consecutive measurements, at least 24 hours apart, over a 7-day period. In the DLT assessment period, subjects who experience FBS >200 mg/dL must have testing repeated within 7 days.

3.2.4. Definition of Maximum Tolerated Dose, Maximum Administered Dose, and Recommended Phase 2 Dose

The estimated MTD is the dose level associated with approximately 30% of DLT-evaluable subjects experiencing a DLT. The target interval for the DLT rate is 25%-35%. Due to the discreteness of the dose levels and in the interest of the safety of subjects, the estimated MTD is the highest tested dose level with a DLT rate $\leq 35\%$ in at least 6-12 DLT-evaluable subjects. In general, the highest dose in Part 1 that provides an acceptable safety profile (MTD or MAD) will also be the highest dose tested in Part 2 unless one or more of the following suggest that an alternate (ie, lower) dose would be preferable:

- Clinically significant anti-tumor effects observed at a lower dose.
- The frequent occurrence of late and relevant AEs that occur after the DLT period.

The MAD is declared without an MTD based on the highest dose level with an observed DLT rate $<25\%$ (the lower bound of the MTD range) and where sufficient safety and efficacy signals have been observed.

The RP2D is the dose chosen for further study based on assessment of a favorable benefit-risk profile across the totality of Phase 1 study results, including both Parts 1 and 2. The RP2D will

take into account late and relevant toxicities that occur after the DLT assessment period in Part 1 and/or the safety/tolerability of multiple cycles of treatment.

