Grade 3 thrombocytopenia without resolution to \leq Grade 2 within 1 week	Withhold dose until resolution to \leq Grade 2; no dose adjustment for subsequent cycles
Grade 4 thrombocytopenia or Grade 3 thrombocytopenia accompanied by clinically significant bleeding	Withhold dose until resolution of bleeding and/or thrombocytopenia to \leq Grade 2: 
• Dose reduce KZR-261 by one level if within a cycle• Subsequent cycles will begin at the reduced dose level

Abbreviations: NCI CTCAE=Common Terminology Criteria for Adverse Events

Table 4: Dose Modifications for Neutropenia

NCI CTCAE Grade	Dose Adjustment
≤Grade 3 neutropenia	No dose adjustment for subsequent cycles
Grade 4 neutropenia (duration <7 days) with resolution to ≤Grade 2 within 1 week	No dose adjustment for subsequent cycles
Grade 4 neutropenia (duration ≥7 days)	
 Withhold dose until ≤Grade 2 Reduce dose by one level if within a cycle, and begin subsequent cycles at the reduced dose level
Second episode of Grade 4 neutropenia (duration ≥7 days)	
 Withhold dose until ≤Grade 2 Reduce dose by one additional level if within a cycle, and begin subsequent cycles at the reduced dose level
Grade 3 or 4 neutropenia accompanied by fever (≥38.3°C)	
 Withhold dose until afebrile with resolution of neutropenia to ≤Grade 2 within 1 week; resume dosing without dose reduction. For a second episode of febrile neutropenia, reduce dose by one level if within a cycle, and begin subsequent cycles at the reduced dose level.

Abbreviations: NCI CTCAE=National Cancer Institute Common Terminology Criteria for Adverse Events

Table 5: Dose Modifications for Pancreatic Toxicity

NCI CTCAE Grade	Dose Adjustment
Amylase or lipase ≥Grade 3	Discontinue KZR-261
Hyperglycemia ≤Grade 1; amylase, lipase Grade 1 or Grade 2 without any symptoms.	No dose adjustment for subsequent cycles
Hyperglycemia ≥Grade 2 (ie, requiring treatment)	Withhold dose until ≤Grade 1, then: 
 Resume KZR-261 at the same dose or dose reduce one level if within a cycle Begin subsequent cycles at the same or reduced dose level

Abbreviations: NCI CTCAE=National Cancer Institute Common Terminology Criteria for Adverse Events

Table 6: Dose Modifications for Ocular Toxicity

NCI CTCAE Grade	Dose Adjustment

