6.1.5. Missed Doses

Study treatment should be administered within the visit windows as per the Schedule of Events ([Appendix A](#) and [Appendix B](#)), with an exception for delays in dosing for up to 7 days duration for resolution of toxicity. Missed doses as a result of patient non-compliance will be considered protocol deviations.

Subjects who do not fulfill treatment interruption criteria ([Section 6.1.2](#)) or meet Individual Subject Stopping Rules ([Section 8.1.2](#)) may miss up to 2 consecutive doses or up to 6 doses in total over the first 6 cycles for any reason (eg, AE, scheduling, emergency). Subjects who require more than two dose reductions, or who miss one entire cycle because of an AE(s) must permanently discontinue KZR-261. Missed doses due to implementation of Study Stopping Rules ([Section 8.1.1](#)) should be discussed with the Medical Monitor to evaluate whether KZR-261 should be discontinued.

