7.2.8. Clinical Laboratory Evaluations

Collection of blood and urine samples for clinical laboratory evaluations are outlined in the Schedule of Events for Cycles 1 and 2 ([Appendix A](#)) and Cycle 3+ ([Appendix B](#)).

Clinical laboratory tests for safety (hematology, serum chemistries, urinalyses, coagulation tests, serum pregnancy) and other tests during scheduled visits will be performed at the clinical trial site or an alternative, licensed local testing facility. Pregnancy tests, urine or serum, may be performed at the study site using a licensed test. Abnormal safety laboratory results that are considered clinically significant should be repeated as soon as possible (preferably within 24–48 hours).

Subjects who are HBsAg negative and hepatitis B core antibody positive with no detectable DNA at Screening will require regular monitoring of hepatitis B virus DNA at the discretion of the Investigator.

Unscheduled or additional laboratory tests with results reported by local laboratories may be performed if immediate results are necessary for management of treatment-emergent AEs or dosing determination. Unless otherwise noted, when scheduled simultaneously with a dosing visit, results of laboratory evaluations should be reviewed prior to administration of study drug.

Detailed instructions for sample collection, processing, storage, and shipment will be provided in the Laboratory Manual. It is recommended that the smallest appropriate sampling tubes be used for local laboratory sample collection to curtail blood loss due to phlebotomy.

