7.2.8.2. Serum Chemistry

Blood samples for serum chemistry testing will be collected at timepoints detailed in the Schedule of Events ([Appendix A](#) and [Appendix B](#)) while the subject is in a fasting state (no food or caloric drinks after an overnight fast or other fasting period lasting at least 6 hours). Clinical chemistry parameters shown in [Table 9](#) will be analyzed according to standard methods at a local laboratory.

Table 9: Clinical Chemistry Tests

Serum Chemistry Tests (Fasting)

• Creatinine• Blood urea nitrogen (BUN)• Aspartate aminotransferase (AST)• Alanine aminotransferase (ALT)• Alkaline phosphatase (AP)• Total bilirubin• Serum albumin• Serum total protein• Sodium• Bicarbonate (HCO_3)• Potassium• Chloride• Glucose• Phosphate (PO_4)• Calcium• Amylase• Lipase• Triglycerides

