13. APPENDICES

APPENDIX A. SCHEDULE OF EVENTS FOR SCREENING AND CYCLES 1 & 2

Study Period	Screening ^a	Pre-Treatment (Baseline)	Treatment Period										Treatment Period									
			Cycle 1 ^q										Cycle 2 ^q									
Cycle	D-28 to D-1	D0 to D1	D1	D2	D3 ^t	D5 ^t	D8	D15	D16	D22	D28 ^p	D1 ^p	D2	D3 ^t	D5 ^t	D8	D15	D16	D22	D28 ^p		
Day					+1	+1	±1	±3			±3	+3	+1		+1	+1	±1	±3		±3	+3	
Visit Window (days)																						
Informed consent form	X																					
Inclusion/exclusion criteria	X																					
Hepatitis B and C testing	X																					
Medical history	X																					
ECOG PS	X	X											X	X								X
Physical examination ^b	X	X					X	X		X	X	X					X	X		X	X	
Slit lamp exam and visual acuity ^s	X												X	X								X
Pregnancy test ^c	X	X											X	X								X
Vital sign measurement and oxygen saturation ^d	X	X	X	X			X	X	X	X	X	X					X	X	X	X	X	
12-lead ECG ^e	X	X	X	X			X	X	X		X	X	X				X	X	X		X	
Hematology (Table 8)	X	X					X	X		X	X	X					X	X		X	X	
Serum chemistry (fasting) ^g (Table 9)	X	X					X	X		X	X	X					X	X		X	X	
HgbA1c ^r		X																				
Coagulation parameters ^g (Table 10)	X												X	X								X
Urinalysis ^h	X												X	X								X
PSA ⁱ		X											X	X								X
Tumor markers ^j	X												X	X								X
Tumor imaging and measurements ^k	X																					
PK ^l																						

Study Period	Screening ^a	Pre-Treatment (Baseline)	Treatment Period										Treatment Period										
			Cycle 1 ^q										Cycle 2 ^q										
Cycle	D-28 to D-1	D0 to D1	D1	D2	D3 ^t	D5 ^t	D8	D15	D16	D22	D28 ^p	D1 ^p	D2	D3 ^t	D5 ^t	D8	D15	D16	D22	D28 ^p			
Day					+1	+1	±1	±3		±3	+3	+1		+1	+1	±1	±3		±3	+3			
Visit Window (days)					X	X	X	X	X	X		X	X	X	X	X	X	X	X				
Part 1					X	X	X	X	X	X		X	X	X	X	X	X	X	X				
Part 2					X	X		X	X														
Pharmacodynamic & biological studies ^m					X	X		X	X	X		X	X										X
Circulating tumor DNA ⁿ					X								X	X									X
Tumor biopsy or submission of tumor specimen ^f			X																				X
KZR-261 treatment ^o					X			X	X				X						X	X			
Concomitant medications			X		X	X		X	X	X	X	X	X	X	X	X		X	X	X	X	X	
AE and SAEs			X																				

AEs collected through 30 days after last KZR-261 dose.

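### The fasting-glucose conditions on the 100% dose-increment tier cannot be tested with the glucose samples scheduled in Cycle 1

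*Protocol*

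**What the plan says.** Protocol Section 3.2.1.1 sets tiers for the next dose increment: up to 100%, 50% or 33%, with about 25% also possible. Two of the conditions on the 100% tier concern fasting blood sugar (FBS). No subject may have had FBS above 200 mg/dL on two consecutive measures over 72 hours after dosing, and none may have had FBS above 160 mg/dL "three or more times over a 72-hour period after dosing".

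Glucose is part of the fasting chemistry panel. Section 7.2.8.2 says that blood for "serum chemistry testing will be collected at timepoints detailed in the Schedule of Events". In Appendix A the row "Serum chemistry (fasting") is marked at Screening, Baseline, and Days 8, 15, 22 and 28 of Cycle 1. It is blank on Days 2, 3, 5 and 16. Doses are given on Days 1, 8 and 15 (Section 6.1). For draws on a dosing visit, Section 7.2.8 says "results of laboratory evaluations should be reviewed prior to administration of study drug".

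Two repeat rules exist. Section 3.2.3 says "subjects who experience FBS >200 mg/dL must have testing repeated within 7 days". Section 7.2.8 asks for results judged clinically significant to be repeated, preferably within 24 to 48 hours.

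**The concern.** The two glucose patterns need at least two and at least three samples inside a 72-hour post-dose window, and the schedule does not supply them. Because the tier asks that no subject showed the pattern, a cohort with no samples in the window passes. The SRC could then record a first-in-human safety condition as satisfied when nothing was measured.

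The signal is one the sponsor had reason to watch. Section 1.2.3.1 reports hyperglycemia with pancreatic changes in monkeys after IV bolus dosing. It adds that a "30-minute IV infusion rather than an IV bolus reduced elevations in glucose". This trial infuses over 30 to 60 minutes, so the risk is lower than the bolus data suggest.

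The exposed range is mainly 160 to 200 mg/dL. Around and above 200 mg/dL other rules act: the FBS dose-limiting toxicity (Section 3.2.3), the within-cycle hold (Section 6.1.2) and the criterion for starting a new cycle (Section 6.1.3). Below that, the Table 5 row "Hyperglycemia ≥Grade 2 (ie, requiring treatment") could act. Under Section 6.1.4, however, those modifications apply in Part 1 only from Cycle 2, after the Cycle 1 data on which the SRC decides.

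**Working it through.** The plan gives no figure for this point, so there is nothing to reproduce. The check counts scheduled draws inside each post-dose window.

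**Inputs**
- Doses on Days 1, 8 and 15 (Protocol Section 6.1).
- Scheduled post-baseline chemistry in Cycle 1, with windows: Day 8 ±1, Day 15 ±3, Day 22 ±3, Day 28 +3 (Appendix A). The extracted table is broken, but its Cycle 1 columns align: the vital-signs row is blank on Days 3 and 5, as its footnote says it should be.
- Holds of up to 7 days: Section 6.1.5 permits "delays in dosing for up to 7 days duration for resolution of toxicity".

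**Counting rule.** A draw on day t counts for a dose on day d if d < t ≤ d + 3. A draw on the dosing day is pre-dose and does not count.

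**Nominal days.** The windows are Days 2–4, 9–11 and 16–18. The draws are on Days 8, 15, 22 and 28. None falls inside any window.

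**Visit windows, no hold.** Day 8 can fall on 3 days, Day 15 on 7, Day 22 on 7 and Day 28 on 4, giving 3 × 7 × 7 × 4 = 588 combinations. The maximum is 1 after the second dose (dose on Day 9, next visit on Day 12, exactly 72 h) and 1 after the third (for example, dose on Day 16 and next visit on Day 19).

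**Holds of 0 to 7 days added.** The maximum is 2. It needs the second dose at the Day 9 visit held the full 7 days, to Day 9 + 7 = Day 16. The Day 15 visit chemistry must then fall on Day 17 or 18 and the Day 22 visit on Day 19.

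| Scheduled draws within 72 h | After dose 1 | After dose 2 | After dose 3 |
|---|---|---|---|
| Nominal days | 0 | 0 | 0 |
| Maximum, visit windows | 0 | 1 | 1 |
| Maximum, windows and holds | 0 | 2 | 1 |
| Needed for >200 pattern | 2 | 2 | 2 |
| Needed for >160 pattern | 3 | 3 | 3 |

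**Repeat testing.** Both repeat rules need a first abnormal value, and on nominal days no scheduled draw in the window can supply one. The mandatory repeat applies only above 200 mg/dL and allows 7 days, longer than the 72-hour window.

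**Which escalation steps use this tier.** From SAP Table 2, the step sizes are 3.6/1.8 = +100%, 7.2/3.6 = +100%, 12/7.2 = +66.7%, 18/12 = +50%, 27/18 = +50%, 40/27 = +48.1%, 60/40 = +50% and 80/60 = +33.3%. Only the first three exceed 50%. They end at 12 mg/m², below the monkey highest non-severely toxic dose of 15 mg/m² (Section 1.2.3.1).

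**With glucose added on Days 2, 3 (+1) and 16.** Nominal counts become 2, 0 and 1. Over all visit windows without holds there are always 2 after dose 1 (Day 2, and Day 3 or 4), 0–1 after dose 2 and 1–2 after dose 3.

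**The case against.** The strongest reply is that the protocol permits more glucose testing than the schedule shows. Section 7.2.8 allows unscheduled tests for managing adverse events or deciding on dosing, and Section 6.1.4.1 requires the FBS criteria to be met before each dose. This narrows the gap without closing it. The unscheduled tests are optional, and the pre-dose check looks at the wrong side of the infusion.

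A second reply is that the 72-hour period might mean any 72-hour span once treatment has started, as the FBS dose-limiting toxicity uses a 7-day span not tied to a dose. A high weekly value with a prompt repeat could then trigger the 200 mg/dL condition. That is a fair point for that condition. It does not help the 160 mg/dL condition, because any 72-hour span holds at most two scheduled Cycle 1 draws. The neighbouring amylase and lipase condition, which counts hours after dosing, also favours reading the span from a dose.

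A third reply is that the consequences are small, and most of it stands. Three listed steps are affected, all at low doses, and the documents do not say whether those cohorts are already complete. The tier's other conditions still apply. The SRC may choose a smaller step, including about 25% for related adverse events not otherwise described, and it sees the weekly fasting values. The Laboratory Manual (Section 7.1) and the SRC Charter (Section 3.5) were not available and might add draws or procedures, although Section 7.2.8.2 assigns chemistry timing to the Schedule of Events.

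Finally, the proposed remedy replaces three values above 160 mg/dL with two, which is stricter and is the sponsor's choice to make. Requiring post-dose glucose before any step above 50% would also work, but it would still have to be scheduled. Deleting the condition would be consistent but would remove a safeguard the sponsor chose to include.

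**Conclusion.** The concern holds. On scheduled Cycle 1 draws, the 160 mg/dL condition can never be triggered, and the 200 mg/dL condition cannot be triggered without a dose hold. Absent unscheduled glucose, both count as met by default. This is a mismatch between Section 3.2.1.1 and Appendix A, and it should be corrected.

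Its practical weight is modest. It bears on three of the eight listed steps plus any added cohort using the tier, and mainly on glucose between 160 and 200 mg/dL. If cohorts 1 to 3 are complete, the benefit falls to added cohorts and to correct recording of what was assessed.

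The conclusion assumes that the 72 hours run from a dose, that the Cycle 1 columns of Appendix A are read correctly, and that the Laboratory Manual adds no routine post-dose glucose.

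**What to change.** Add fasting glucose at the existing Part 1 Cycle 1 visits on Day 2 (24 h), Day 3 (48 h) and Day 16 (24 h after the Day 15 dose). The 200 mg/dL condition then works as written after the first dose.

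Restate the 160 mg/dL condition to match the samples, for example treatment-emergent FBS above 160 mg/dL on both Day 2 and Day 3. Define treatment-emergent against baseline, for example baseline FBS of 160 mg/dL or less, because Inclusion Criterion 9 admits values up to just under 200 mg/dL and Exclusion Criterion 7 bars only diabetes that is not well controlled. Day 16 gives the SRC one value to review. If it exceeds 200 mg/dL, the Section 3.2.3 repeat follows.

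State that where these values were not obtained, the SRC records the condition as not assessed and does not treat it as met.

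The cost is three glucose tubes per Part 1 subject, at visits that already include a blood draw, with fasting on those days, plus a protocol amendment with ethics approval. For cohorts 1 to 3 at 2 to 4 subjects each, that is 3 × 2 × 3 = 18 to 3 × 4 × 3 = 36 tubes. Sampling can be limited to cohorts from which a step above 50% is contemplated. No existing visit falls within 72 hours after the Day 8 dose on nominal days, so that interval stays unsampled.

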3.2.2. Intra-subject Dose Escalation

Intra-subject dose escalation will be permitted after consultation with the Medical Monitor and in the following circumstance only:

- Subject must have completed at least two 28-day cycles of treatment (Cycles 1 and 2).
- Subject who experienced an AE* \leq Grade 3 with resolution to Grade 1 or baseline in the setting of a documented tumor response or stable disease over 2 consecutive assessment timepoints. For subjects who experienced a Grade 3 AE, the Investigator and Medical Monitor should come to an unequivocal consensus that the potential benefit of an increase in dose is likely to outweigh the risks.
- Subject must not have experienced a DLT.

- Subject must not have experienced a dose reduction for purposes of managing AEs and/or laboratory abnormalities.
- The higher dose cohort to which the subject would be escalated has been deemed by the SRC to be safe and adequately tolerated.

** AEs must be assessed as unrelated to study treatment, such as intercurrent illness or concomitant medication. AEs that are assessed as related to study treatment would disqualify a patient from dose escalation.*

3.2.3. Definition of Dose-Limiting Toxicity for Part 1

A DLT is defined as an AE or abnormal laboratory value that occurs during the first 28 days of treatment (Cycle 1) and meets the criteria listed below, unless it is assessed to be related to the disease under study, intercurrent illness, or concomitant medications.

Toxicities will be assessed by the Investigator using the NCI CTCAE v5.0. AEs that are not listed in the NCI CTCAE are to be assessed using the criteria in [Section 9.1.2](#). The attribution of an AE is to be assessed by the Investigator using the criteria in [Section 9.1.3](#).

Subjects who experience a DLT in Part 1, Cycle 1 must be withdrawn from study treatment and will not be replaced. Subjects enrolled in Part 1 who discontinue from study treatment for reasons other than a DLT prior to completion of the DLT assessment period ([Section 3.2.3](#)) may be replaced. AEs that meet the definition of a DLT that are reported after Cycle 1 will be taken into consideration for dose escalation decisions and to help determine the dose for further investigation in Part 2.

Subjects who do not experience a DLT in Part 1, Cycle 1 (Dose Escalation) must receive all of their scheduled doses (Days 1, 8, and 15) with completed follow-up data available through 28 days of Cycle 1 to be eligible for DLT assessment. Subjects in Part 1, Cycle 1 who miss a dose for non-AE-related reasons will be replaced.

Both hematologic and non-hematologic DLTs include the following:

- Any AE that prevents the subject from receiving all planned doses during Cycle 1 (Doses may be held up to 7 days for resolution of non-DLT toxicity).
- Any AE that delays the initiation of Cycle 2 by >7 days because the AE has not resolved per criteria required for initiation of a new cycle ([Section 6.1.2](#) and [Section 6.1.4](#)).

Hematologic DLTs include the following:

- Grade 3 or 4 neutropenia (absolute neutrophil count [ANC] <1.0 × 10⁹/L) with a single temperature of >101°F (38.3°C), or microbiologically or radiographically documented infection.
- Grade 4 neutropenia (ANC <0.5 × 10⁹/L) in the absence of fever or infection lasting >7 consecutive days (complete blood count with differential must be measured every 2 to 3 days until recovery of ANC to ≤Grade 2).

- Grade 4 thrombocytopenia (platelet [PLT] count $<25 \times 10^9/L$) lasting >7 days (platelet counts must be measured every 2 to 3 days until recovery to \leq Grade 2 thrombocytopenia).
- Grade 3 or 4 thrombocytopenia (PLT count $<50 \times 10^9/L$) associated with clinically significant bleeding requiring platelet transfusion.

Non-hematologic DLTs include the following:

- Any non-hematologic AE \geq Grade 3, except the following:
 - Nausea, vomiting, diarrhea, electrolyte/metabolic abnormalities, constipation, fever, fatigue, or skin rash that resolves to \leq Grade 2 within 72 hours in the setting of optimal supportive care.
 - Grade 3 elevation in amylase or lipase without clinical or imaging manifestations of acute pancreatitis. In contrast, Grade 4 elevation in amylase or lipase and symptomatic Grade 3 lipase or amylase elevation are considered DLTs.
- Clinical signs and symptoms of acute pancreatitis.
- Drug-induced liver injury (Hy's law), including all of the following: greater than $3 \times$ ULN elevation in aspartate aminotransferase (AST) and/or alanine aminotransferase (ALT), total bilirubin $>2 \times$ ULN in the absence of findings of cholestasis (ie, absence of alkaline phosphatase elevation to $>2 \times$ ULN) AND no other etiology to explain the combination of increased ALT/AST and total bilirubin.
- FBS >200 mg/dL on 2 consecutive measurements, at least 24 hours apart, over a 7-day period. In the DLT assessment period, subjects who experience FBS >200 mg/dL must have testing repeated within 7 days.

3.2.4. Definition of Maximum Tolerated Dose, Maximum Administered Dose, and Recommended Phase 2 Dose

The estimated MTD is the dose level associated with approximately 30% of DLT-evaluable subjects experiencing a DLT. The target interval for the DLT rate is 25%-35%. Due to the discreteness of the dose levels and in the interest of the safety of subjects, the estimated MTD is the highest tested dose level with a DLT rate $\leq 35\%$ in at least 6-12 DLT-evaluable subjects. In general, the highest dose in Part 1 that provides an acceptable safety profile (MTD or MAD) will also be the highest dose tested in Part 2 unless one or more of the following suggest that an alternate (ie, lower) dose would be preferable:

- Clinically significant anti-tumor effects observed at a lower dose.
- The frequent occurrence of late and relevant AEs that occur after the DLT period.

The MAD is declared without an MTD based on the highest dose level with an observed DLT rate $<25\%$ (the lower bound of the MTD range) and where sufficient safety and efficacy signals have been observed.

The RP2D is the dose chosen for further study based on assessment of a favorable benefit-risk profile across the totality of Phase 1 study results, including both Parts 1 and 2. The RP2D will

take into account late and relevant toxicities that occur after the DLT assessment period in Part 1 and/or the safety/tolerability of multiple cycles of treatment.

